## 8.7.1 Primary efficacy endpoint and analysis

For Phase IIa part the primary endpoint is the Overall response rate (ORR) which is the proportion of patients, whose best overall response is either CR or PR, confirmed at least 4 weeks after initial documentation. A test proportion with normal approximation to the binomial distribution will be used and null hypothesis will be rejected if 8 or more responses are observed in the 30 evaluable patients (26.7% of responders or more)

#### 8.7.2 Secondary efficacy endpoints and analyses

The following secondary efficacy endpoints will be considered:

- Disease control rate (DCR) is the proportion of patients whose best overall response is either CR, PR, or SD.
- 4-month (18-week) DCR is proportion of patients whose best overall response is either CR, PR, or SD 4 months after D1 (using tumor assessments before Day 127).
- The Time to Progression (TTP) is the time from Day 1 to the date of first documented radiographic tumor progression. TTP does not include deaths. If a patient has not had a TTP event at the cut-off date for analysis, TTP will be censored at the date of last evaluable tumor assessment before the cut-off.
- Progression Free Survival (PFS) is the time from Day 1 to the date of first documented tumor progression or death due to any cause, whichever occurs first. If a patient has not had a PFS event and is not known to have died at the cut-off date for analysis, PFS will be censored at the date of last evaluable tumor assessment before the cut-off.
- Overall Survival (OS) is the time from Day 1 to the date of death due to any cause. If a
  patient is not known to have died at the cut-off date for analysis, survival will be censored
  at the date of last contact.
- Duration of overall Response (DoR) applies only to patients whose best overall response is CR or PR. The start date is the date of first documented response (CR or PR) and the end date is the date of first documented disease progression or the date of death due to underlying cancer. DoR will be censored if progression or death due to underlying cancer is not observed at the cut-off date for the analysis, or death to another cause than underlying cancer or start of further anti-cancer therapy. The censoring date will be the date of the last

evaluable tumor assessment.

- Tumor size (in mm) is defined as the sum of the diameters recorded for all target lesions as identified at baseline. Relative change from baseline in tumor size over time will be summarized and graphically represented. This value is automatically calculated in "Follow-up target lesions" form of eCRF.
- HBV DNA and HCV DNA viral load (and change from baseline) will be summarized for each visit.

For OS, the percent survivors over time will also be presented considering the proportions of patients alive at 6, 9, 12, 18, and 24 months, along with corresponding 95% CIs. At these timepoints the restricted mean survival time with 95% CI will be calculated.

For PFS, the percent of non-progressors over time will also be presented considering the proportions of patients having not progressed at 6, 9, 12, 18, and 24 months, along with corresponding 95% CIs. At these timepoints the restricted mean non-progression time with 95% CI will be calculated.

For Tumor size, a graphical representation will be done using a waterfall plot. This plot will display the best percentage change from baseline for each patient, sorted in descending order (using bar) and colored by the Best Overall Response (CR/PR/SD/PD).

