# Secondary objectives for Phase I and Phase IIa

Disease control rate (DCR) is the proportion of patients whose best overall response during their participation in the study is either CR, PR, or SD. It will be presented using percentage and exact 95% confidence interval. 4-month (18-week) DCR is proportion of patients whose best overall response in the study is either CR, PR, or SD 4 months after D1.

The Time to Progression (TTP) is the time from Day 1 to the date of first documented radiographic tumor progression. TTP does not include deaths. If a patient has not had a TTP event at the cut-off date for analysis, TTP will be censored at the date of last evaluable tumor assessment before the cut-off.

Progression Free Survival (PFS) is the time from Day 1 to the date of first documented tumor progression or death due to any cause, whichever occurs first. If a patient has not had a PFS event at the cut-off date for analysis, PFS will be censored at the date of last evaluable tumor assessment before the cut-off.

Overall Survival (OS) is the time from Day 1 to the date of death due to any cause. If a patient is not known to have died at the cut-off date for analysis, survival will be censored at the date of last contact.

Duration of overall Response (DoR) applies only to patients whose best overall response is CR or PR. The start date is the date of first documented response (CR or PR) and the end date is the date of first documented disease progression or the date of death due to underlying cancer. DoR will be censored if progression or death due to underlying cancer is not observed at the cut-off date for the analysis or start of further antineoplastic therapy. The censoring date will be the date of the last evaluable tumor assessment.

TTP, PFS, OS and DoR will be presented using the number of events, number of censored patients, quartiles TTP/PFS/OS/DoR (Q1, median and Q3) and the associated confidence interval. A graphical representation will be done for these four outcomes using a Kaplan-Meier curve with 95% confidence interval.

For OS, the percent survivors over time will also be presented considering the proportions of patients alive at 6, 9, 12, 18, and 24 months, along with corresponding 95% CIs.

For PFS, the percent non-progressors over time will also be presented considering the proportions of patients having not progressed at 6, 9, 12, 18, and 24 months, along with corresponding 95% CIs.

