## 7.7.2 Derived variables

The following conventions will be used:

- 1 month corresponds to 365.25/12=30.4375 days.
- 1 year corresponds to 365.25 days.

The following variables will be calculated:

• Age expressed in years: the age at informed consent form (ICF) signature presented in whole years (rounded down to the whole year)

INT([date of ICF signature - date of birth +1]/365.25)

- Body Mass Index (BMI) expressed in kg/m^2: Weight (kg) / Height (m^2)
- Duration of an event expressed in days: End date Start date + 1

The following survival variables will be calculated:

- TTP expressed in months = (Date of first documented radiographic tumor progression date of first treatment administration +1)/30.4375
  - Or (Date of last evaluable tumor assessment date of first treatment administration +1)/ 30.4375 in case of censoring.
- PFS expressed in months = (MIN(Date of first documented radiographic tumor progression, Date of death from any cause) date of first treatment administration +1)/30.4375
  - Or, (Date of last evaluable tumor assessment date of first treatment administration +1)/30.4375 in case of censoring.
- OS expressed in months = (Date of death from any cause date of first treatment administration + 1)/30.4375
  - Or, (Date of last contact date of first treatment administration +1) /30.4375 in case of censoring.
- DoR expressed in months for patients whose best overall response was CR or PR = (MIN(Date of first documented disease progression, date of death from underlying disease)
   Date of first documented response +1)/30.4375
  - Or, (Date of the last evaluable tumor assessment Date of first documented response +1)/30.4375 in case of censoring.

The following variables will be derived for Pexa-Vec and Nivolumab treatment information:

• Duration of IMP exposure: expressed in weeks and calculated as

[(Date of last IMP administration) - (Date of first IMP administration) +1]/7

• Relative Dose Intensity (%): expressed as a percentage and defined as the ratio of "delivered" to the "planned" dose intensity. The dose intensity is the total amount of IMP given a fixed unit of time. A Relative Dose Intensity of 100% indicates that the IMP was administered at the dose planned per protocol, without delay and without cancellations. It is calculated as

100 x IMP Actual Dose Intensity / IMP Planned Dose Intensity

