# 8.7 Analysis of efficacy

All the efficacy analyses will be based on the PP population which is the primary dataset and will be analyzed and presented by Cohort (Cohort #1, Cohort #-1 and overall). Efficacy analyses will be repeated for ITT population for Phase IIa and for DLT population for Phase I.

All efficacy variables will be listed in dedicated listings by subject and the following summaries will be presented by Cohort (Cohort #1, Cohort #-1 and overall) in case of de-escalation in any part of the study:

- Continuous efficacy endpoints will be summarized using N, Mean, sd, Median, interquartile range (Q1-Q3), MIN, and MAX. If appropriate, log-normal variable will be log-transformed for descriptive statistics.
- Categorical efficacy endpoints will be summarized using number and percentage (with exact 95% CI).

 Survival efficacy endpoints will be presented using the number of events, number and percentage of censored patients, quartiles (Q1, median and Q3) and the associated 95% CI.
 A graphical representation will be done for these endpoints using a Kaplan-Meier curve with 95% CI.

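### DoR censors deaths not attributed to the cancer and gives no attribution rule; if a responder dies this way before progression, Kaplan-Meier DoR is biased upwards and disagrees with PFS

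*SAP*

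**What the plan says.** **Event.** In protocol 12.3.3, for patients whose best response is CR or PR, "the end date is the date of first documented disease progression or the date of death due to underlying cancer". The synopsis and protocol 8.1, under their definitions of radiological endpoints, carry the same rule, and so does SAP 8.7.2.

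**Censoring.** The protocol says "DoR will be censored if progression or death due to underlying cancer is not observed at the cut-off date for the analysis", or at the start of further antineoplastic therapy. Censoring of other deaths is only implied there. SAP 8.7.2 makes it explicit by adding "death to another cause than underlying cancer or start of further anti-cancer therapy" to the reasons. On timing it says "The censoring date will be the date of the last" evaluable tumor assessment.

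**Derivation.** SAP 7.7.2 computes the end of response as "MIN(Date of first documented disease progression, date of death from underlying disease"). The term here is the underlying disease, not the underlying cancer.

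**Contrast.** PFS in SAP 8.7.2 runs to "first documented tumor progression or death due to any cause, whichever occurs first". TTP, in the same list, leaves deaths out altogether.

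**Estimator.** SAP 8.7 reports event and censoring counts, quartiles and 95% CIs for the time-to-event endpoints, and adds: "A graphical representation will be done for these endpoints using a Kaplan-Meier curve with 95% CI". The methods text describes no competing-risk estimate, no sensitivity analysis counting all deaths, and no rule for deciding whether a death is due to the cancer. The list of tables is not readable in the public copy, so it could not be checked.

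**The concern.** A responder who dies can no longer be in response. Kaplan-Meier assumes that a censored patient has the same later risk of ending response as those still followed. For a patient who has died this is untrue, so the censoring is informative and the curve sits too high.

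The outcome also depends on a judgement that the plan does not define. A death from decompensated cirrhosis may be ascribed to the tumor, the liver disease or the treatment. SAP 8.7.2 and SAP 7.7.2 could class it differently, and in an open-label single-arm trial whoever attributes the death may know the patient's response.

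The protocol itself makes such deaths conceivable:

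- Section 1.1.1 says that about 90% of HCC arises in liver disease, chiefly cirrhosis.
- Section 1.7 anticipates effects on liver function, especially in cirrhotic patients, and a possible rise in myocarditis risk.
- Appendix 3 reports fatal immune-mediated pneumonitis in 5 of 691 nivolumab patients.

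At stake is how durability is read. Protocol 1.4.1.1.2 and 1.6 present the prolonged responses on nivolumab alone as a leading signal, so readers will compare this trial's DoR with them. Under the planned rule, a death from toxicity would tend to lengthen that DoR.

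**Working it through.** The documents state no DoR figure, so there is none to reproduce.

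**1. One patient under each definition.** Take a responder with no progression who dies between two scans.

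| Cause as judged | PFS | DoR, SAP 8.7.2 | DoR, SAP 7.7.2 |
|---|---|---|---|
| Cancer | event | event | event |
| Cirrhosis or liver failure, not the tumor | event | censored at last scan | event if cirrhosis counts as underlying disease, otherwise censored |
| Treatment toxicity | event | censored at last scan | censored at last scan |

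**2. Number of responders.** From the hypotheses in SAP 7.1: 30 × 0.15 = 4.5 under H0 and 30 × 0.35 = 10.5 under H1.

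**3. Bias under constant hazards.** Let λ be the total hazard of ending response, and let q be the share of first DoR-ending events that are non-cancer deaths. The documents give no q, so it is an assumption.

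- Any-cause median = ln 2 / λ.
- Planned median = ln 2 / [λ(1 − q)].
- Ratio = 1/(1 − q): 1/0.95 = 1.05, 1/0.90 = 1.11, 1/0.80 = 1.25, 1/0.70 = 1.43.
- At q = 0 the ratio is 1.

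**4. Effect of the scan schedule.** A simulation used exponential times, scans every 6 weeks to 12 months and every 12 weeks after that, progression dated at the next scan, and non-cancer deaths censored at the last scan. The true any-cause medians of 6, 9 and 12 months are assumed. The large-sample columns come from 100,000 responders. The last columns come from 3,000 runs of 10 responders, cut off at 24 months.

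| Assumed median | q | Planned median, large sample | Any-cause median, large sample | n = 10: planned higher | n = 10: equal |
|---|---|---|---|---|---|
| 6 | 10% | 6.9 | 6.9 | 39% | 61% |
| 6 | 20% | 8.3 | 6.9 | 62% | 38% |
| 6 | 30% | 9.7 | 6.9 | 78% | 22% |
| 9 | 10% | 11.0 | 9.7 | 36% | 64% |
| 9 | 20% | 12.4 | 9.7 | 64% | 36% |
| 9 | 30% | 15.2 | 9.7 | 80% | 20% |
| 12 | 10% | 15.2 | 12.4 | 38% | 62% |
| 12 | 20% | 15.2 | 12.4 | 63% | 37% |
| 12 | 30% | 17.9 | 12.4 | 78% | 22% |

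The planned median was lower in no run.

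**5. Why one death may not show.** Take 10 responders, distinct times, no other censoring, and the median as the first time the curve is at or below 0.5. Counting every death, that is the 5th time (5/10).

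- If the 2nd ending is a censored death, the curve is 0.9 after the 1st, then 0.9 × 7/8 × 6/7 × 5/6 = 0.5625 at the 5th and 0.5625 × 4/5 = 0.45 at the 6th. The median moves by one position.
- If the censored death is the 8th ending, the median is the 5th time under both rules.

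**The case against.** The best defence is that this is a prespecified choice of what to estimate. The cause-specific event appears in three places in the protocol and again in SAP 8.7.2. TTP goes further by ignoring deaths, so tumor-specific and all-cause endpoints are planned side by side. That one patient can be a PFS event and a DoR censoring follows from the definitions and is not in itself a contradiction. This much stands. It does not settle the matter, because TTP already serves as the endpoint that excludes deaths, while DoR counts some deaths and drops others by an undefined attribution that the SAP words in two ways.

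The impact is also limited, and that stands too:

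- Entry requires Child-Pugh A, ECOG 0 or 1 and a life expectancy of at least 3 months, and excludes recent moderate or severe ascites, variceal bleeding and encephalopathy. The 90% figure is general epidemiology, not a description of this trial's patients.
- DoR is a descriptive secondary endpoint. SAP 7.4 names DCR, TTP and survival, not DoR, as what is weighed before the combination is abandoned.
- Efficacy data and fatal AEs are listed by patient, so with some ten responders a careful reader could find such a death.

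A reader might infer that a responder who dies is carried forward as still responding. The SAP does not do that: follow-up stops at the last evaluable scan, and the bias comes from the later risk that Kaplan-Meier then assumes. Nor is every liver-failure death censored, since one attributed to the cancer is an event.

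**Conclusion.** The concern holds conditionally. If a responder dies before progression from a cause judged not to be the cancer, the planned Kaplan-Meier DoR is biased upwards and treats that patient differently from PFS. Separately, and whether or not such a death occurs, SAP 7.7.2 and 8.7.2 use different terms and neither document says how a death is to be attributed.

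The size depends on q, which the documents do not supply. The factors of 1.05 to 1.43 assume constant hazards and q between 5% and 30%; they illustrate and do not predict. A reader might take them as the expected overstatement, or suppose that one such death must visibly shift the median. Neither is supported: the bias is zero without such a death, and with 10 responders at q = 10% the two medians coincided in 61–64% of runs.

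ORR, its test, the interim stopping rules, PFS and OS do not use this definition and are unaffected. The point is worth correcting but does not threaten the primary analysis.

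**What to change.** Define the DoR event as progression or death from any cause. Make the change in SAP 7.7.2 and 8.7.2, and in every place where the protocol gives the definition: the synopsis, section 8.1 and section 12.3.3. Changing only some of these would create a new inconsistency. Delete non-cancer death from the censoring reasons in SAP 8.7.2, and keep censoring at the last evaluable assessment before new anti-cancer therapy or the cut-off. Attribution then no longer matters for this endpoint.

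If the sponsor prefers not to amend the protocol for this, add the any-cause version to the SAP as a prespecified analysis reported beside the current one, and settle on one term in SAP 7.7.2 and 8.7.2 with a short rule for how cause of death is assigned.

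The cost is small. PFS and OS already need every death date, so no new data are required. The full change needs protocol wording at the next amendment, and reported DoR may be slightly shorter.

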## 8.7.3 Exploratory efficacy endpoints and analyses

Some exploratory analyses could be done using the following statistical methods:

- A Linear regression to study potential effects of covariates on continuous endpoints
- A logistic regression to study potential effects of covariates on categorical endpoints (such as ORR and DCR)
- A Log-rank test and/or a Cox model to study potential effects of covariates on survival endpoints (PFS, TTP, OS and DoR). Estimates of the HRs with 95% CIs will be obtained from a Cox regression model.

# 8.8 Analysis of safety

All the safety analyses will be performed on the SAF population which is the primary dataset for safety evaluation in Phase I and Phase IIa parts. Safety analyses will be repeated on DLT population in Phase I part.

#### 8.8.1 Adverse Events

#### 8.8.1.1 Definitions

From the date of signature of ICF and up to first IMP administration (i.e. before the patient receives any IMP) only SARs caused by a protocol-required procedure (e.g., related to invasive procedures such as blood sampling) will be collected and reported. AEs, SAEs, or procedure related ARs that occur during this period, and that are considered by the investigator as relevant to the patient condition, will be collected as a current medical history.

After the initiation of either IMP and up to 28 days after the last dose of IMP, all AEs and SAEs will be collected and recorded on the eCRF. SAEs will also be reported to Transgene.

SAEs occurring more than 28 days after the last dose of IMP, and evaluated by the Investigator as related to the IMP will be collected and reported to Transgene indefinitely even after end of study. Only SAEs occurring prior to end of study will be reported in the eCRF.

All AEs will be coded using the Medical Dictionary for Regulatory Activities (MedDRA) central coding dictionary using latest version available. NCI-CTCAE version 4.03, dated June 14, 2010 will be used.

All AEs will be reported on the "Adverse Event" section of eCRF.

Dose-limiting toxicity (DLT) is defined as any of the following treatment-related adverse events (AEs) and occurring during the first 4 weeks (up to D29), in the Phase I part of the study; grades are referring to NCI CTCAE v. 4.03:

- 1. All Grade 3-4 non-hematologic toxicity that represent a 2-grade increase over baseline, excluding:
  - Untreated or inadequately treated nausea, vomiting and diarrhea,
  - Untreated or inadequately treated fever > 40.0°C lasting less than 24 hours (Grade
     3); only fever > 40.0°C lasting more than 24 hours (Grade 4) qualifies for DLT
  - Alopecia,
  - Grade 3 fatigue that returns to grade 2 or less within 7 days.
  - Grade 3 laboratory/metabolic abnormalities, other than ALT or AST, that are not considered clinically significant and that return to grade 2 or less within 72 hours.
- 2. Any Grade ≥ 3 treatment-related acute immune-related AE involving major organs, such as: immune-related pneumonitis, colitis, nephritis, hepatitis, endocrinopathies, immune-related rash and other rare but severe immune-related reactions.

- 3. Grade  $\geq$  3 injection site reaction.
- 4. AST or ALT  $\geq$  10xULN, even if asymptomatic, unless it is related to a definite progression of liver metastases or another clearly identifiable etiology; doubling of AST or ALT that is concurrent with a doubling of the total bilirubin.
- 5. Any toxicity at least possibly related to study therapy that results in a delay in treatment of 2 or more weeks.

# 6. Hematological:

- Grade  $\geq 3$  or  $\geq 2$ -grade increase over baseline of neutropenia lasting for more than 7 days.
- Neutropenic fever.
- Grade 4 thrombocytopenia or grade 3 thrombocytopenia with clinically significant bleeding.
- 7. Cardiac: association of the 3 following cardiac abnormalities
  - Left ventricular ejection fraction (LVEF) less than the lower limit of normal (LLN), as assessed by echocardiography and symptomatic due to drop in ejection fraction, responsive to intervention,
  - Increase of blood troponin T or I above the upper limit of normal (ULN),
  - Any ECG abnormality consistent with a Grade 3 cardiac disorder.

#### 8.8.1.2 AEs Analysis

## Adverse Event (AE)

For the analyses, the number and percentage of patients will be summarized in a frequency table by body system organ class (SOC) and preferred terms (PT) as per MedDRA dictionary. The number of events will be also summarized in the same table. The table will be displayed by SOC sorted alphabetically and by PT within SOC sorted by decreasing count according to the overall column. Each patient will be counted only once within each classification (SOC / PT).

## AEs subject to Immediate Reporting

AEs subject to immediate reporting are the AEs with the item "Event subject to immediate reporting" ticked "Yes" in "Adverse Event" form of the eCRF.

## Serious Adverse Events (SAEs)

The SAEs are the adverse events with the item "Is this adverse event considered as Serious?" ticked "Yes" in "Adverse Event" form of the eCRF. If the item is missing, the AE will be considered

as Serious.

## AEs related to Study procedure

AEs related to Study Procedure are the AEs with the item "Is this event related to study procedure?" ticked "Yes" in "Adverse Event" form of the eCRF. If the data is missing, the AE will be considered as related to Study Procedure.

